### Sample size and power

This is a pilot RCT, and the primary outcomes of this study are: 1) to test the feasibility and acceptability of the crowdsourced intervention, and 2) to pilot the preliminary impact of crowdsourced PS intervention in promoting HIV testing among partners of the newly identified HIV cases. In addition, this pilot RCT aimed to collect preliminary data for the designing of a full RCT, which aimed to measure the efficacy of the crowdsourced PS intervention in promoting PS. Thus, the sample size of this study is not designed and will be not powered enough to test the difference between the two arms. However, with a sample size of 120 (80 for intervention arm and 40 for the control arm, respectively), this pilot study would collect enough information to measure the feasibility and acceptability of the intervention, and it will be able to observe the differences between the two arms and collect preliminary data for an adequate sample size calculation of a full RCT. With a sample size of 120 (ratio of 2:1), alpha=0.05, power=0.80, and the partner return rate in the conventional PS arm is 30% (around 31% in 2016 in Guangzhou), the minimal detectable effect size would be 26.7% for this pilot study.

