## **Study measures and outcomes**

### **Primary outcomes**

The primary outcomes are: 1), the feasibility of the study and the feasibility of the intervention. The feasibility of the study will be measured in the ability to enroll 120 newly identified MSM HIV cases as index participants in the study center in a 12-month period, and the ability to

contact the index MSM (follow-up rate) and their partners at 3 months after enrolment (proportion of the surveyed partners response to the survey). The feasibility of the intervention will be used to measure whether the crowdsourced intervention is successfully used or carried out. This will be measured in the frequency of the partners in the intervention arm receiving the crowdsourced intervention and the frequency of the partners taking action after they receive the intervention (whether go for HIV testing). 2), the acceptability of the crowdsourced intervention: this will be measured at baseline among index participants and the partners of the index participants in the intervention arm. We will ask the index participants and their partners whether the crowdsourced intervention is acceptable to them. 3), the preliminary impact of the intervention: the proportion of partners returning for HIV testing within 3 months of the index participant's enrolment in the study, determined based on the partners presenting to the centers and those verified from the CDC electronic medical record central database.

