## **Secondary outcomes**

Secondary outcomes will include: 1) The proportion of partners being notified by indexes among all reported partners; 2) the number of tested partners, normalized to the number of index participants (i.e. the mean number of partners getting notified per index participant); 3) the proportion of positive HIV tests among tested partners; 4) the number of tested partners with a positive HIV test, normalized to the number of index participants (i.e. the mean number of partners with HIV per index participant); 5) the proportion of reported partners getting HIV testing who are not spouses or regular partners, and 6) the proportion of condom use by presenting partners during the last anal intercourse.

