## **Additional measures**

In addition to the primary and secondary outcomes, we will collect index and presenting partners' socio-demographics, sexual orientation, sexual orientation disclosure status, HIV and other STDs testing history and HIV PS history.

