## Statistical Analysis Plan

For the primary outcomes of feasibility and acceptability of the intervention: this will be analyzed through descriptive analysis to assess the feedback on the feasibility and acceptability of the crowdsourced PS intervention among index MSM and their partners in the intervention group. For the primary outcome of the proportion of partners returning for HIV testing within 3 months of the index participant's enrolment in the study, log-binomial regression (generalized linear model with binomial distribution and log link) will be used to calculate 95% confidence intervals for the proportion of notifiable partners visiting by arm. Risk differences and risk ratios will also be calculated in these models. As this study is a pilot RCT, and we will only recruit 120 index MSM, and they will be randomly assigned in a 2:1 ratio, adjustment for covariates would be necessary if the two study arms are not balanced. In secondary analyses, we will adjust for pre-specified potential confounding variables that might bias the estimate if not accounted for (e.g. index age, index marital status). If a partner reports more than one index referred him, he will be counted as a returning partner for each identified index.

*Table 1* Analysis strategies for secondary outcomes

Secondary Outcome	Population	Model Type
The proportion of reported partners being notified by indexes among all reported partners	Reported sexual partners	Binomial regression, robust variance
Mean number of partners tested per index participant	Index participants	Poisson or negative binomial regression, robust variance
The proportion of positive HIV tests among tested partners	Tested sexual partners	Binomial regression, robust variance
Mean number of partners with HIV (case-finding) per index participant	Index participants	Poisson or negative binomial regression, robust variance
The proportion of reported partners getting HIV testing who are not spouses or regular partners	Reported casual male sexual partners	Binomial regression, robust variance
The proportion of presenting partners reporting condom use during the last anal intercourse	Presenting sexual partners	Binomial regression, robust variance

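### Secondary outcomes 3 and 4 do not separate new diagnoses from known-positive partners who re-test, so case-finding yield and positivity can be overstated

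*Combined protocol and SAP*

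**What the plan says.** Two secondary outcomes count HIV-positive partners. Outcome 3 is the share of tested partners whose test is positive. Outcome 4 is "the number of tested partners with a positive HIV test, normalized to the number of index participants". Table 1 of the Statistical Analysis Plan analyses outcome 4 among index participants by Poisson or negative binomial regression and names it "Mean number of partners with HIV (case-finding) per index participant". It analyses outcome 3 by binomial regression among all tested sexual partners.

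Neither definition refers to earlier HIV status. The requirement of a recent diagnosis appears only under Eligibility, where it applies to the index men.

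Two planned data sources could show an earlier diagnosis:

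- Under Additional measures, index participants and presenting partners are asked for their "HIV and other STDs testing history".
- Under Primary outcomes, testing is established from partners who present and "those verified from the CDC electronic medical record central database".

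No analysis rule uses either source to sort positives into new and known.

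**The concern.** The sexual partners of newly diagnosed men may include men who already know they are positive. If such a man receives a message or card, comes to the centre and tests again, his result enters outcomes 3 and 4 on the same footing as a first diagnosis. Yet Table 1 calls outcome 4 case-finding, and the Background justifies partner services partly by their ability to identify new cases. A count that mixes the two groups does not measure that.

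What is at stake is mainly the next trial. The last paragraph of the Statistical Analysis Plan says that the pilot will show which secondary outcomes are worth carrying forward and will supply the inputs for its sample size. The Summary adds that the full trial is to assess cost-effectiveness. A yield per index man that includes known cases would make case-finding look more productive than it is.

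**Working it through.** **The plan's own figure.** The plan gives no expected value for outcomes 3 or 4. Its only power figure concerns the primary outcome: "With a sample size of 120 (ratio of 2:1), alpha=0.05, power=0.80", control return rate 30%, minimal detectable effect 26.7 points.

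It reproduces with a two-sided pooled test of 40 against 80:

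- Pooled proportion = (40 × 0.30 + 80 × 0.567)/120 = 0.478.
- Null SE = √(0.478 × 0.522 × (1/40 + 1/80)) = 0.0967.
- Alternative SE = √(0.30 × 0.70/40 + 0.567 × 0.433/80) = 0.0912.
- z = (0.267 − 1.96 × 0.0967)/0.0912 = 0.85, so power is 0.802.

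The figure is sound but has no bearing on how positives are classified.

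**Inputs for the illustration.** None of these is in the documents, so all are assumptions:

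- k: share of partners already diagnosed, 8% or 15%.
- r: share of those who re-test, 0%, 10% or 30%.
- u: share of the remaining partners who are tested, 40% (30% in one variant).
- v: share of those tested who are newly found positive, 10% (20% in the same variant).

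The Background gives 8.0% as HIV prevalence among MSM in China in 2015. That is not the share of named partners already diagnosed, so 8% here is only a convenient value.

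**Formulas, per 100 partners.**

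- New cases = 100 × (1 − k) × u × v
- Known positives counted = 100 × k × r
- Inflation of outcome 4 = known/new
- Outcome 3 as defined = (known + new)/(100 × (1 − k) × u + 100 × k × r). Restricted to new diagnoses it equals v.

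**Worked case** (k = 8%, r = 10%, u = 40%, v = 10%).

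- New = 100 × 0.92 × 0.40 × 0.10 = 3.68.
- Known = 100 × 0.08 × 0.10 = 0.80.
- Inflation = 0.80/3.68 = 22%.
- Outcome 3 = 4.48/(36.8 + 0.8) = 11.9%, against 10.0%.

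**Range.**

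| k | r | u | v | Known | New | Inflation of outcome 4 | Outcome 3 as defined | Outcome 3, new only |
|---|---|---|---|---|---|---|---|---|
| 8% | 0% | 40% | 10% | 0 | 3.68 | 0% | 10.0% | 10% |
| 8% | 10% | 40% | 10% | 0.80 | 3.68 | 22% | 11.9% | 10% |
| 8% | 30% | 40% | 10% | 2.40 | 3.68 | 65% | 15.5% | 10% |
| 15% | 10% | 40% | 10% | 1.50 | 3.40 | 44% | 13.8% | 10% |
| 15% | 30% | 40% | 10% | 4.50 | 3.40 | 132% | 20.5% | 10% |
| 8% | 10% | 30% | 20% | 0.80 | 5.52 | 14% | 22.3% | 20% |

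The direction is fixed: once r exceeds zero, both outcomes rise, because every known positive who re-tests adds a positive result. The size depends entirely on the assumed inputs.

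**The case against.** The best defence is that the plan never promises new infections. Its hypothesis is more partners with confirmed HIV, and a known positive who re-tests does have confirmed HIV. This is also a pilot, stated not to be powered to compare the arms, and these are secondary outcomes. That limits the weight of the point but does not remove it: the word case-finding invites reading the count as new cases, and the pilot's results feed the design of the full trial.

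A second objection is that the size is unknown and could be nil. That stands in full.

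A reader might go further and infer that known positives also depress the primary outcome, because they stay in the denominator without testing. The documents do not support this:

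- The Statistical Analysis Plan analyses *notifiable* partners and does not define the term, so inclusion of known positives is not established.
- Understatement needs known positives to test less often than other partners. Observed uptake is (1 − k)u + kr. With u = r = 30% it is 30% for any k. With k = 8% and r = 50% it is 0.276 + 0.040 = 31.6%, an overstatement.
- At r = 0 and k = 8% in both arms, 30% becomes 27.6%, but a risk ratio of 0.567/0.30 = 1.89 is unchanged. At r = 0 the case-finding error also vanishes, so the worst cases of the two effects cannot occur together.
- Removing such partners would need their HIV status, which is not among the listed baseline items, or database matching of men who never present, which the plan does not describe.

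A reader might also infer that the error differs by arm because the intervention offers more delivery routes. That is possible, but nothing in the documents shows that these routes draw in known positives at a different rate.

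**Conclusion.** The point holds for secondary outcomes 3 and 4 only. As written, the plan counts a re-tested known-positive partner as a positive in both outcomes, and Table 1 labels the second case-finding. If any such partner re-tests, both overstate new diagnoses.

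The size cannot be derived from the documents. It is 22% under the worked assumptions and 0% if nobody known to be positive re-tests. The other rows of the table show only how strongly it depends on the inputs.

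No conclusion follows that testing uptake is understated or that the comparison between arms is biased. The matter is worth correcting before analysis because the remedy is small and the results inform the full trial.

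**What to change.** 1. Define outcomes 3 and 4 on new diagnoses: a positive test in a partner with no positive test before the index's enrolment.
2. Classify tested partners by the testing history already planned for presenting partners and, where available, by the CDC database, using the same rule in both arms. State which source prevails if they disagree, and show positives that neither source can classify as a separate line.
3. For outcome 3, remove known positives from both numerator and denominator. For outcome 4, keep all index participants and change only what is counted.
4. Report all positives alongside, so that the hypothesis on confirmed HIV can still be read as written.
5. Leave the primary testing denominator unchanged.

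The cost is a few sentences in the SAP, a check that the partner questionnaire records the result and date of earlier tests, and a date check in a database already named as a source. The downside is some misclassification: self-report may conceal an earlier diagnosis, records may be incomplete, and a partner tested elsewhere may have no questionnaire history.

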## **Summary and Impact**

HIV PS is underused among key populations around the world, and crowdsourced PS could potentially enhance the effectiveness of PS. Innovative approaches to designing PS interventions are needed, yet many HIV campaigns repackage old ideas. Crowdsourcing leverages the high internet use and willingness to participate in online forums among MSM to transform the design and implementation of partner services. Upon completion of the study, we will provide the scientific community with a strategy to develop crowdsourced PS interventions, and test its feasibility and acceptability. In addition, this pilot study can reform the existing HIV PS for MSM, and assess the preliminary impact of the crowdsourced intervention, which will be helpful for designing a full RCT, which aimed to evaluate the efficacy and cost-effectiveness of the intervention. If successful, this strategy has the strong potential to be implemented in similar countries/regions.

## **Ethical approvals**

The study was reviewed and approved by the Institutional Review Boards at the Guangzhou Center for Diseases Control and Prevention (IRB#2019001).

